## **4.9 Screening**

### Primary objective: Web-based recruitment screener:

Participants who click on the banner advertisements will be taken to an online screening survey, hosted on SurveyGizmo.com, which will include the eligibility script and questions from the RCT Participant Eligibility Screener. For those who meet eligibility criteria, we will ask for a first name, email address, and phone number. For those who do not meet eligibility criteria, there will be an option to provide a first name and email address if they want to be contacted about future studies. Those individuals who initially screened ineligible because they did not report having anal sex with a man in the past 6 months will be re-contacted to take the online screener again. Web-based screening instruments allow for real-time data collection across multiple outreach modes (e.g., banner ads, flyers, in-person outreach) pooled into a single stream. We will use Secure Socket Layer (SSL) encryption for transfers of information online and data will be stored in the secure, HIPAA-compliant servers of SurveyGizmo. The Emory AC team maintains a business partner HIPAA agreement with SurveyGizmo.

### Secondary objective: web-based recruitment screener:

Participants who have clicked on an online ad or saw an ad in person for the study will be directed to an online screening survey hosted by Qualtrics. The survey will include the eligibility script and questions found in the Mystery Shopper Participant Eligibility Screener. Analogous to SurveyGizmo, Qualtrics abides by HIPAA rules to ensure that data are properly protected and best security practices followed. Qualtrics safeguards all customer data, and uses secure data centers to ensure the highest protection as per the Health Information Technology for Economic and Clinical Health Act requirements.

## **5.0 STUDY PROCEDURES**

### **5.1 Enrollment Procedures**

For the primary objective, eligible participants (as identified by screener) will be contacted by email and/or phone, and invited to the SRV in their city. Once at the SRV, study staff will consent the participants, randomize the participants, and then provide a computer for the participants to complete the baseline survey. Once they have consented, participants will be considered formally enrolled in the study. After completion of the baseline survey, study staff will assist participants with accessing the WebApp, creating a strong but memorable password, and bookmarking the WebApp (if participants choose to). If more than 30 days occurs between screening and the baseline visit, eligibility will be re-determined at the baseline visit.

For the secondary objective, eligible participants (as identified by screener) will be contacted by the study team to schedule an interview. If the individual is deemed capable and willing, they will be consented by a member of the study team.

For the tertiary objective, eligible participants will be contacted by calling the site or the site director directly (if contact information is available) to schedule an interview.

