## STUDY ABSTRACT

- DESIGN:** *A two-arm prospective randomized controlled trial (RCT) in Philadelphia, Houston, and Atlanta. Participants randomized to the control condition will only see the site locator portion of the Get Connected intervention website. It will include information on HIV prevention services. Participants randomized to the intervention condition will receive tailored online content specific to their demographic characteristics (e.g., age, race/ethnicity, location, and relationship status), HIV/STI risk behaviors (e.g., HIV/STI testing history; substance use; communication with partners regarding status) and sociocultural context (e.g., homelessness, incarceration). We will also recruit, enroll, and train 10-15 mystery shoppers per city to conduct a mystery shopper assessment. Two mystery shoppers will visit each testing site separately and complete a standardized assessment of their visit. Site directors from 10 randomly selected testing sites in each city will be interviewed to assess sites' satisfaction with the biannual performance assessments and their improvements in service delivery when working with YMSM.*
- DURATION:** *Mystery shoppers are enrolled for approximately six months, or the time it takes them to complete approximately ten site visits. YMSM participating in the RCT are enrolled for 12 months.*
- SAMPLE SIZE:** *Total study sample size is 480 with the aim of maintaining a randomized sample of approximately 400 online-recruited and retained YMSM for 12 months. After consent, but prior to completion of the baseline survey, YMSM are randomized to either the intervention (n=240) or control (n=240) condition.*
- POPULATION:** *Individuals who were assigned male at birth and currently identify as male. 15-24 year-old (inclusive), self-report as HIV-negative or sero-status unaware, speak and read English, live in Philadelphia, Houston, or Atlanta, and meet one or both of the following high risk criteria: have not received HIV testing in past six months and/or report having consensual anal sex with a man in the past six months.*
- STRATIFICATION:** *Each site (Houston, Atlanta, and Philadelphia) will enroll 160 YMSM and 10-15 mystery shoppers.*

**DATA  
COLLECTION:**

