### 2.4 Study Hypotheses/Research Questions

- *Relative to the control condition, YMSM exposed to the GC intervention will report significantly greater increases in routine HIV/STI testing over a 12-month period. HIV testing will be the primary outcome for the trial.*
- *Relative to the control condition, YMSM exposed to the GC intervention will report increases in motivation around HIV testing (conceptualized as HIV/STI testing intentions, self-efficacy to engage in HIV/STI testing, and overcoming testing-related barriers).*
- *Relative to the control condition, YMSM exposed to the GC intervention will report significantly greater PrEP awareness and willingness to use PrEP).*

The primary analyses of the data from the Get Connected 2-parallel group randomized clinical trial will be performed according to the participants' original treatment assignment (i.e., intention-

to-treat analyses) and the inclusion of all data from all participants randomized in the final analysis.

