### 3.4 Study Randomization, Stratification, or Description of Non-Random Assignment Procedures

For the primary objective, participants will be randomly assigned to one of two groups, stratified by city/SRV site: intervention and control. After consent, YMSM are randomized to either the control or intervention condition (Intervention, n=240; Control, n=240). **We intend to blind participants to the intervention arm assignment in order to improve the internal validity of the study, the rigor of the assessment of outcomes, and to minimize bias due to awareness of treatment assignment.**

For the secondary objective, mystery shoppers will visit testing sites that have been randomized such that each site has an equal likelihood of being shopped on any given day at any given time (during normal operating hours).

For the tertiary objective, participants will be randomly selected from participating HIV testing sites in each of the three cities. Only sites that have been visited and assessed by study participants will be included in each city's sample for randomization.

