## 5.4 Intervention/Investigation Procedures

### 5.4.1 Get Connected Intervention

Participants will complete a 30- to 45-minute baseline survey that includes questions on lifetime HIV testing history, lifetime STI testing history and knowledge about STIs, date of their most recent STI test (if known), and whether they were ever diagnosed with an STI. GC will use baseline survey data to select and deliver personalized, tailored content to YMSM assigned to the intervention. Furthermore, as part of the participant's baseline visit, study staff will collect contact information where participants may be reached for follow-up assessments. We will use best practices to retain participants (e.g., collecting participant's cell phone number, email address, Facebook, WhatsApp, and/or Skype username, and contact information for 2 peers who could help us contact them). Additional surveys will occur at 1, 3, 6, 9, and 12 months after intervention initiation, and can be completed online. These follow-up surveys will repeat many of the questions from the baseline survey and will also include additional questions on HIV and STI testing in each 3-month period, including test results. These surveys will be the same for participants in the control and intervention arms. For participants in the intervention arm, the GC WebApp will be retailored after each follow-up survey, based on any different information provided on key questions.

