## 10.3 Statistical Analysis Plan

10.3.1 We will use the general framework of generalized linear mixed models (GLMM) to test for intervention effects over time. Note that some of our outcomes are binary, some count and some continuous traits, and thus need to be treated differently. The general form of the GLMM will be  $g(\mu_{ij}) = \beta_0 i + \beta_{cov} Covariates_{ij} + \beta_{Time} j + \beta_{Trt} Trt_{Armi} + \beta_{Arm \times Time}$ , where  $\beta$  is the mean response corresponding to subject  $i$  at Time  $j$  (baseline and 4 follow-ups), with its appropriate link function (identity for continuous outcome, logit for binary outcome and natural log for count outcomes);  $Trt = 1$  if the  $i$ -th subject is in the intervention group and 0 if the  $i$ -th subject is in the attention-control group. The interaction coefficients are of interest here, measuring the difference in the rate of change in outcome across the two treatment groups over time. The subject-specific random intercepts are assumed to be normally distributed with a common variance and they account for within-person correlation. We will also explore if we need a subject-specific random-slope corresponding to visit in the above model. Maximum likelihood estimation will be used for fixed effect parameters. Models will be compared according to information criterion like AIC, BIC. For some binary outcomes like HIV testing, we will perform an aggregate analysis after collapsing across the repeated measures using simple logistic regression comparing whether the probability of having tested at least once over the entire FU period is different across treatment groups, after adjusting for baseline values. To ensure robustness, we will also apply an exchangeable working correlation structure to its corresponding generalized estimating equation (GEE) model. We will also conduct exploratory regression analyses to examine city differences in the outcomes. These regressions will be run with group assignment and city in the model, controlling for socio-demographic characteristics.

Interactions between group assignment and city will be tested to explore potential site-specific moderators of treatment effect.

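### Randomisation comes before the baseline survey, so the baseline values used in the Section 10 analyses and for tailoring are collected after allocation, and a randomised participant can have none

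*Combined protocol and SAP*

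**What the plan says.** The order of events appears in two places. Section 5.1 says that "study staff will consent the participants, randomize the participants, and then provide a computer for the participants to complete the baseline survey". The abstract, under sample size, says: "After consent, but prior to completion of the baseline survey, YMSM are randomized". Sections 3.4 and 5.3 place randomisation after consent and are consistent with this. No section puts the survey first.

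The intervention is reached later in the visit: "After completion of the baseline survey, study staff will assist participants with accessing the WebApp" (Section 5.1). On blinding, Section 3.4 states an intention for participants only: "We intend to blind participants to the intervention arm assignment". It says nothing about the staff who run the visit.

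The survey has two uses:

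- **Tailoring** (Section 5.4.1): "GC will use baseline survey data to select and deliver personalized, tailored content to YMSM assigned to the intervention".
- **Analysis.** Section 10.3 includes baseline as a time point in the mixed model and runs an aggregate logistic regression "after adjusting for baseline values". Section 10.1 adjusts for, and tests interactions with, socio-demographic characteristics, substance use and psychological distress. Section 6.1.1 lists all three as baseline measures.

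The analysis set in Section 2.4 is intention to treat, with "inclusion of all data from all participants randomized in the final analysis".

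**The concern.** A baseline covariate is safe to adjust for because allocation cannot have influenced it. That holds automatically when the covariate is recorded before allocation. When it is recorded afterwards, it holds only if nobody who can affect the answers, or whether the survey is finished, knows the arm. This plan gives up the automatic protection and does not describe a full substitute.

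The order also lets someone enter the randomised set before supplying any data. Such a participant counts under intention to treat but has no completed baseline for the adjusted models. In the intervention arm, the content has nothing to be tailored to, and the plan describes WebApp set-up only after the survey is complete.

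What is at stake is the integrity of the baseline-adjusted and change-over-time analyses in Section 10, and delivery of the intervention to everyone assigned to it.

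**Working it through.** The plan states no figure on this point, so the check is to trace where the baseline survey is used and see which analyses the order can reach.

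**Step 1. Sequence, from Section 5.1.** Consent, randomise, baseline survey (30 to 45 minutes, Section 5.4.1), WebApp access. All take place at one visit to the recruitment venue.

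**Step 2. Which components use the baseline survey.**

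| Component | Uses baseline survey? |
|---|---|
| Section 2.4 GEE for HIV testing: arm, time, arm by time, five follow-ups | No |
| Section 2.4 Z-test of frequent-tester proportions | No |
| Section 10.1 regression on arm alone | No |
| Section 10.1 adjusted regressions and moderator interactions | Yes: socio-demographics, substance use, distress |
| Section 10.1 comparison of participant characteristics between arms | Yes |
| Section 10.3 mixed model | Yes: baseline is a time point |
| Section 10.3 aggregate logistic regression | Yes: baseline adjustment |
| Section 10.3 exploratory city models | Yes: socio-demographic covariates |
| Section 5.4.1 tailoring | Yes: intervention arm only |

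The exposure lies in the Section 10 analyses that use baseline and in tailoring. It does not reach the two Section 2.4 tests of HIV testing.

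**Step 3. What stands between allocation and the baseline answers.** Participants are meant to be blind, see no intervention content before the survey, and enter their own answers (Sections 7.3.3 and 11.3.1). The remaining route is through staff. Study staff randomise and set up the WebApp (Section 5.1), and site study staff log participants into the baseline survey (Section 3.1, Phase 1c). Whether staff can see the arm before the survey is submitted is not stated.

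**Step 4. What happens to a randomised participant with no completed baseline.** Section 6.1.3 covers withdrawal after the baseline survey, not during it. Section 10.4 gives a general rule for missing covariates: complete cases if few are affected, otherwise some form of imputation. Applied to the adjusted models, the first branch would drop randomised participants from those models. No rule addresses this group specifically.

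**Step 5. Does anything require randomising first?** Stratification is by city or venue only (Section 5.3), which is known on arrival. Tailored content needs the survey answers. Nothing in the design depends on allocation preceding the survey.

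**The case against.** The strongest defence is that little can go wrong in practice. The survey is self-administered, participants are meant to be blind and have seen no content, and much of it asks for factual history. The two Section 2.4 tests of HIV testing ignore baseline, and Section 10.1 also fits a model with arm alone. The survey is paid ($20, Section 8.2) and follows consent at the same visit, so few people may stop partway. All of this stands and it keeps the point modest. It does not make the baseline a pre-allocation measurement, and it does not fill the gaps in Steps 3 and 4.

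A reader might go further in three ways that the documents do not support.

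- **That staff are unblinded, or that one person performs every step.** The text refers only to study staff or site study staff. It does not say that the arm is displayed before the survey. Silence on concealment is a gap in the plan, not evidence of unblinding.
- **That the trial's HIV-testing result is biased.** The Section 2.4 GEE and Z-test contain no baseline covariate, so contaminated baseline values cannot enter them.
- **That early stoppers cut power by a known amount.** Assume a 25% control rate (Section 10.2 gives none), the planned 13-point difference, and a share f of participants counted as untreated, so that the difference becomes 0.13 × (1 − f). A two-sided pooled Z-test at 0.05 with 200 per arm gives power 0.80, 0.76 and 0.72 for f = 0, 5% and 10%. But 5% and 10% of the 480 randomised are 24 and 48 people, while 200 per arm is the number left after planned attrition. Stoppers who give no outcome already belong to that planned loss, so the remaining 400 are not diluted. If all 480 are kept, the denominator is 240 per arm and power is 0.87, 0.83 and 0.79. Both the control rate and f are assumptions. The documents give no stopping rate, so none of these figures measures the harm.

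**Conclusion.** The point holds as a design weakness of limited reach. The order is explicit in two sections and not contradicted. As a result, baseline values in the Section 10 mixed model, aggregate logistic regression, and covariate and moderator models are collected after allocation, as are the tailoring data. Concealment from site staff until submission is not described, and randomised participants without a completed baseline have no specific rule.

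No size can be attached. Bias would require knowledge of the arm to affect the answers or completion of the survey, and the documents give nothing from which to estimate that. The number who would stop during the survey is also not given. Confidence is high on the sequence and on which analyses use baseline. Whether any actual bias would occur is unknown. The reason to act is that the protection is cheap and the present order serves no stated purpose.

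**What to change.** In Sections 5.1, 5.3 and 3.4 and in the abstract, set the order within the same visit as:

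1. consent;
2. baseline survey completed and submitted;
3. randomisation, with the allocation generated or released only after submission;
4. WebApp access.

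Section 5.1 treats consent as formal enrolment. The text should therefore also say that the target of 480 counts randomised participants, and that those who consent but do not submit are reported separately. Section 10.4 is still needed for single unanswered items, because participants may decline most questions they find uncomfortable (Section 11.3.1).

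The cost is a wording change, a release trigger in the randomisation system (which the documents do not describe), and replacement of participants who do not submit the survey. No extra visit is needed.

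If the order has to stay, the minimum is a statement that staff do not learn the arm until the survey is submitted, plus a rule in Sections 6.1.3 and 10.4 for randomised participants with no completed baseline. That would address staff influence and the missing rule, but early stoppers would still enter the randomised set.

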## **5.2 Locator/Contact Information**

For the primary objective, at the participant's baseline study visit, study staff will collect participants' contact information for follow-up assessments: this information will be entered into SMART (Study Management and Retention Tool). We will collect each participant's cell phone number, email address, as well as encourage them to share their Facebook, WhatsApp, and/or Skype usernames, and/or contact information for 2 peers who could help us contact them in the event the participant cannot be reached. Participants will be asked if messages can be left at the peers' numbers they provided. Study staff will not leave messages unless expressly permitted to do so by the participant. If permission is given to leave messages, site staff will assure participants that messages left with peers will only ask for the participant to contact study staff and will not include any protected health information or information related to study participation. Peer contact information will be maintained using the same confidential data management practices used for all study data.

For the secondary objective, participants will be asked if they would like to be contacted by email, phone, or text message for site visit reminders and other study communication. If participant selects the phone option, the study team will ask for explicit permission to leave voice messages that will not include any protected health information or information related to study participation. Participant contact information will be maintained using the same confidential data management practices used for all study data.

## **5.3 Randomization Procedures**

For the primary objective, after consent, YMSM are randomized to either the control or intervention condition, stratified by city/SRV site (Intervention, n=240; Control, n=240). Participants will be randomized on a 1:1 basis to either the control or intervention arm.

For the secondary objective, testing sites are randomized by day of the week and time of day. After consent and training, participants will work with study staff to find day and time slots for their site visits.

For the tertiary objective, 10 eligible testing sites in each city will be randomly selected. The site director for those sites will be contacted for an interview.

## 5.4 Intervention/Investigation Procedures

### 5.4.1 Get Connected Intervention

Participants will complete a 30- to 45-minute baseline survey that includes questions on lifetime HIV testing history, lifetime STI testing history and knowledge about STIs, date of their most recent STI test (if known), and whether they were ever diagnosed with an STI. GC will use baseline survey data to select and deliver personalized, tailored content to YMSM assigned to the intervention. Furthermore, as part of the participant's baseline visit, study staff will collect contact information where participants may be reached for follow-up assessments. We will use best practices to retain participants (e.g., collecting participant's cell phone number, email address, Facebook, WhatsApp, and/or Skype username, and contact information for 2 peers who could help us contact them). Additional surveys will occur at 1, 3, 6, 9, and 12 months after intervention initiation, and can be completed online. These follow-up surveys will repeat many of the questions from the baseline survey and will also include additional questions on HIV and STI testing in each 3-month period, including test results. These surveys will be the same for participants in the control and intervention arms. For participants in the intervention arm, the GC WebApp will be retailored after each follow-up survey, based on any different information provided on key questions.

